13.4. Effectiveness endpoint

The change between unaided and aided measurements will be analyzed by means of paired (samples) t-test or Wilcoxon signed rank sum test according to the normal or non-normal distribution or McNemar test for categorical variables where appropriate. Categorical variable comparisons will be performed using a Chi-square test or a Cochran-Mantel-Haenszel test for trend for ordinal variables with 3 or more categories. The mean change will be displayed together with their 95% confidence interval (95%CI).

Analysis of secondary endpoints based on comparisons between groups on continuous measurements will be performed by Student's t-test or non-parametric test (Mann–Whitney U test) for normal and non-normal distributions, respectively. Normality will be assessed by means of Shapiro-Wilks test and the p-value will be reported. Analysis of secondary endpoints based on the change over time (if more than 3 measurements) will be analyzed by means of GEE models or mixed models for continuous outcomes to account for repeated measures using patient as the subject. The dependent variable will be pre-log transformed depending on normal or non-normal distribution. The model will have the clinical outcomes as dependent variables and baseline values, visits and other covariates as explanatory variables. All assumptions for regression models will be assessed by viewing plots of the residual values. The plot for the mean change over time will be reported.

14. Ethics

14.1. Statement(s) of Compliance

- The study shall be conducted in accordance with the protocol and ethical principles that have their origin in the Declaration of Helsinki.
- The study will be conducted in compliance with this protocol, GCP, and 21 CFR 50, 21 CFR 54, and 21 CFR 56.
- The clinical study will not begin at the site until IRB approval is received.

This document is electronically controlled. Printed copies are considered uncontrolled.

Confidential

15. Study Administration

15.1. Monitoring

This study will be conducted and monitored according to the highest scientific and ethical standards, based on standard operating procedures of the Sponsor or designee, and ethics guidelines as required by regulation and law, and as appropriate to the prospective research populations. The following guidance's and regulations have been consulted in preparing the study's protocol and procedures:

-Title 21 of the Code of Federal Regulations (21 CFR) Parts:

- 50 Protection of Human Subjects
- 54 Financial Disclosure by Clinical Investigators
- 56 Institutional Review Boards

Employees of the Sponsor, or its designees, who have received appropriate training, will serve as the Study Monitor(s). Study monitoring activities will include review of completed study documents, source document verification and reporting, verification of database accuracy, and assessment of the completeness and accuracy of the data. A final monitoring report will be prepared to document that all protocol requirements were satisfied. The Study Monitor(s) will also assume responsibility for communications between the Study Investigators and the Sponsor.

15.2. Data Management

All data required for this study will be captured via eCRFs using Oracle Clinical's Remote Data Capture (RDC) module. The associated software and database have been designed to meet regulatory compliance requirements for deployment as part of a validated system compliant with laws and regulations applicable to the conduct of clinical studies that use electronic records and signatures. System backups for data stored in the Oracle Clinical system will be consistent with Medtronic standard procedures.

The Investigator will ensure that all eCRFs are completed promptly, completely, and accurately. Only authorized study personnel are permitted to enter data. These tasks may be delegated by the Investigator as desired and noted on a Delegation of Authority Log. The Sponsor will provide training and instructions to assist with eCRF completion. In the event of data discrepancies, the study center staff will be contacted and asked to resolve queries electronically in the RDC system. Any irresolvable data-related

issues will be routed to the Sponsor for review and final disposition. An audit trail is maintained in Oracle Clinical to capture any corrections or changes of the eCRFs.

Medtronic will only consider eCRFs to be complete when all data discrepancies between source data and eCRFs have been resolved and eCRF content has been reviewed by a Sponsor-representative monitor. In addition, all eCRFs must also be reviewed and electronically signed by the Investigator, indicating his/her agreement with the accuracy of all recorded data. The Investigator will provide his/her electronic signature on the eCRFs.

Prior to data extraction, all collected data will undergo a final verification by Data Management. Documentation of this verification will be maintained in the Sponsor study files. Upon the completion of the verification, data will be extracted and transferred to the appropriate personnel for analysis.

15.3. Direct Access to Source Data/Documents

The Sponsor, its affiliates, IRB, or government officials may audit the study site to evaluate the conduct of the study. The sponsor and its representatives expect to have access to the source data for this study including medical records.

15.4. Confidentiality

The Sponsor and its affiliates may access subject confidential information during the course of the study. Confidentiality of the data shall be observed by all parties at all times throughout the clinical study. All data shall be secured against unauthorized access.

15.5. CIP Amendments

If during the course of the study the Sponsor assesses that an amendment is necessary the Sponsor will follow all applicable internal procedures to amend the protocol, and if applicable, the IC. Any amendments to the protocol or IC will be reviewed and approved by the IRB.

15.6. Record Retention

All documentation generated as a result of this clinical study must be properly prepared and maintained. Records must be maintained by the investigational site for a minimum of two years after study completion. No study document shall be destroyed without prior written agreement between the Sponsor

This document is electronically controlled. Printed copies are considered uncontrolled.

Confidential

and the investigational site. All documentation generated as a result of this clinical study must be properly prepared and maintained. Table 6, below, describes the records and reports to be maintained during and after the study.

15.6.1. Sponsor Requirements

All original hard copy or certified copies and electronic data will be retained by the Sponsor per standard operating policy on documentation retention.

15.6.2. Investigational Site Requirements

All site generated hard copy and electronic data will be retained by the site per specific institutional standard operating policy. Should the investigator wish to assign the study record to another party or move them to another location, the Sponsor must be notified in writing and agree to the change.

This document is electronically controlled. Printed copies are considered uncontrolled.

Confidential

Table 6. Sponsor and Investigator Records and Reports

Records	Maintained by Sponsor	Maintained by Investigator
Device Accountability (shipment/receipt, assignment, destruction, return)	x	x
Case Histories (CRFs, IC/PIS, AE)	x	x
Protocols/Deviations (obsolete, change history record, rationale)	x	x
Agreements (Confidential, Investigator, Consulting)	x	x
Training Records (Sponsor, institution, topic)	x	x
Report	Prepared by Sponsor For	Prepared by Investigator For
Lack of IC/Authorization	N/A	Sponsor, IRB
Unanticipated Serious Adverse Device Effects (USADE)	Investigators, IRB	Sponsor, IRB
Protocol Deviations	N/A	Sponsor, IRB*
Withdrawal of IRB Approval	Investigators, IRB	Sponsor, IRB
Final Report	Investigators, IRB (if required)	IRB (if required)

*In accordance with specific Ethics Committee requirements

15.7. Publication and Use of Information

The Sponsor must be notified of any intent to publish data stemming from this clinical study. Conditions of use of the data are governed by the terms of the Investigator Agreement and Publication Plan.

A description of this clinical trial will be available on <http://www.ClinicalTrials.gov>.

Appendix A: APHAB Version A

Appendix B: Satisfaction Questionnaire

This document is electronically controlled. Printed copies are considered uncontrolled.

Confidential

Appendix A

This document is electronically controlled. Printed copies are considered uncontrolled.

Confidential

Appendix B

This document is electronically controlled. Printed copies are considered uncontrolled.

Confidential

Satisfaction Questionnaire

Name: _____

Date : _____

Please answer the following questions regarding your current use of the Sophono and quality of life.
Please choose only one option for each question:

Overall, how satisfied are you with your Sophono processor?

- Very Satisfied
- Satisfied
- Neutral (Neither Satisfied or Dissatisfied)
- Dissatisfied
- Very Dissatisfied

Would you recommend the Sophono system to another patient with a conductive hearing problem?

- Yes
- No
- Not Sure

How satisfied or dissatisfied are you with the appearance of the hearing device?

- Very Satisfied
- Satisfied
- Neutral (Neither Satisfied or Dissatisfied)
- Dissatisfied
- Very Dissatisfied

This document is electronically controlled. Printed copies are considered uncontrolled.

Confidential

How easy or difficult is it to operate the hearing device as instructed?

- Very Easy
- Easy
- Neutral (Neither Easy or Difficult)
- Difficult
- Very Difficult

Listed below are some Sophono features. For each feature, please indicate how satisfied you are with that feature. Please choose only one option for each question.

Overall comfort of device	 Always  Sometimes  Never
Visibility to others	 Always  Sometimes  Never
Clearness of tone and sounds	 Always  Sometimes  Never
Durability	 Always  Sometimes  Never
Reliability	 Always  Sometimes  Never

This document is electronically controlled. Printed copies are considered uncontrolled.

Confidential

Magnet-spacer strength in day to day activities	 Always  Sometimes  Never
Magnet-spacer strength in physical activities	 Always  Sometimes  Never
Do you use a different strength for physical activities?	 Yes  No
Ability to tell locations of sounds	 Always  Sometimes  Never

This document is electronically controlled. Printed copies are considered uncontrolled.

Confidential

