Indication under investigation	
There is no indication under investigation; this is a post-market study.
 
Below is the currently cleared indication for use:
 
The Otomag™ Alpha 2 Sound Processor is intended for use with the Otomag Headband or Otomag Softband (no age limitations), or with the Otomag Magnetic Implant (patients 5 years of age and up) for the following patients and indications:
 
 • Patients with conductive or mixed hearing losses, who can still benefit from amplification of sound. The pure tone average (PTA) bone conduction (BC) threshold for the indicated ear should be better than 45 dB hearing loss (HL) (measured at 500, 1000, 2000, and 3000 Hz). • Bilateral fitting is applicable for most patients having a symmetrically conductive or mixed HL. The difference between the left and right sides' BC thresholds should be less than 10 dB on average measured at 500, 1000, 2000, and 4000 Hz, or less than 15 dB at individual frequencies. • Patients who have a profound sensorineural hearing loss in one ear and normal hearing in the opposite ear, who for some reason will not or cannot use air conduction (AC) Contralateral Routing of Signal (CROS). The PTA AC threshold of the hearing ear should be better than 20 dB HL (measured at 500, 1000, 2000 and 3000 Hz).
Investigation Purpose	Accumulate post-market clinical evidence for the safety and effectiveness of the Sophono Alpha 2 Maximum Power Output (MPO) systems.

This document is electronically controlled. Printed copies are considered uncontrolled.

Confidential

Product Status	Cleared for use in the geography where study is being conducted (USA).
Primary Objective(s)	
The primary objectives of this study are to
 
 • Assess the safety of the Sophono implant • Assess the effectiveness of the Sophono Alpha 2 MPO processor
Secondary Objective(s)	
The secondary objectives of this study are to
 
 • Compare the effectiveness of the Sophono Alpha 2 processor to the Alpha 2 MPO processor • Assess the effectiveness of the Sophono Alpha 2 and the Sophono Alpha 2 MPO over time • Assess subject satisfaction after system use • Assess Quality of Life (QOL) after system use

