6.1.2. Secondary Objectives

The secondary objectives of this study are to

- Compare the effectiveness of the Sophono Alpha 2 processor to the Alpha 2 MPO processor

This document is electronically controlled. Printed copies are considered uncontrolled.

Confidential

- Assess the effectiveness of the Sophono Alpha 2 and the Sophono Alpha 2 MPO over time
- Assess subject satisfaction after system use
- Assess QOL after system use

in subjects diagnosed with CHL, SSD and mixed HL who currently has or has had the Sophono implant.

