6.2.2. Secondary Endpoints

The secondary endpoints include:

- The difference in the free-field pure tone audiometry assessed by PTA aided by Alpha 2 processor compared to the PTA aided by Alpha 2 MPO processor
- Change over time of PTA in the Sophono Alpha 2 and Alpha 2 MPO
- Subject satisfaction, via non-validated satisfaction questions and QOL assessment through validated Abbreviated Profile of Hearing Aid Benefit (APHAB)TM assessment

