9.1. Study Population

The subject population for this study includes male and female patients who have received the Sophono implant. Subjects will be recruited from Investigators who have implanted Sophono systems or from other non-investigator physician referrals. Subjects are expected to represent a population diagnosed with CHL, SSD, and mixed HL.

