7.10.5 Secondary endpoint#3

The secondary objective #3 and secondary objective #4 will be evaluated as the subject satisfaction, via non-validated satisfaction questions and QOL assessment through validated Abbreviated Profile of Hearing Aid Benefit (APHAB)™ assessment.

The analysis of this endpoint will be performed using descriptive statistics to summarize results of the questionnaires overall and by each item. This will include

mean, standard deviation, median, minimum, and maximum for continuous variables, and counts and percentages for categorical variables.

The data will be summarized on the overall set of patients and by APHAB version (pediatric or adult version).

Table x - Subject Satisfaction and product features

Table x - Quality of Life - APHAB

Table x - Quality of Life – APHAB Adult version

Table x - Quality of Life – APHAB Pediatric version

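### The only recommendation item asks about a conductive hearing problem, so its pooled rate does not show whether subjects with single-sided deafness would recommend the system for their own kind of hearing loss

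*Protocol*

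**What the plan says.** The satisfaction questionnaire (Protocol, Appendix B) has 13 items. The second asks: "Would you recommend the Sophono system to another patient with a conductive hearing problem". The answers are Yes, No and Not Sure. The form as reproduced has no alternative wording, skip instruction or not-applicable option for any diagnosis.

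The secondary objectives, including satisfaction, are set "in subjects diagnosed with CHL, SSD and mixed HL who currently has or has had the Sophono implant" (Protocol 6.1.2). Protocol 9.1 describes the same mix: "Subjects are expected to represent a population diagnosed with CHL, SSD, and mixed HL". Protocol 8.3 refers to the indications for use for the meaning of SSD. The indication listed in the Synopsis for that group reads: "Patients who have a profound sensorineural hearing loss in one ear and normal hearing in the opposite ear".

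Protocol 6.2.2 defines the endpoint as "Subject satisfaction, via non-validated satisfaction questions and QOL assessment through validated Abbreviated Profile of Hearing Aid Benefit". SAP 7.10.5 gives the analysis: "The analysis of this endpoint will be performed using descriptive statistics to summarize results of the questionnaires overall and by each item". The only breakdown named there is this: "The data will be summarized on the overall set of patients and by APHAB version (pediatric or adult version". Subsets by implanted-ear diagnosis appear in SAP 7.10.1, under the primary effectiveness endpoint only.

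**The concern.** The word *another* in the item presupposes that the respondent also has a conductive problem. That holds for conductive loss and, through the conductive component, for mixed loss. It does not hold for an SSD subject, who is asked about a use of the device that he or she has not had.

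For that subject each answer is ambiguous. No or Not Sure may express dissatisfaction, or only lack of knowledge about conductive loss. Yes may be a guess on someone else's behalf. The planned summary puts these answers in the same percentage as answers from subjects whom the item fits. A reader of the report would naturally take that percentage as the proportion of users who would recommend the system to someone like themselves.

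**Working it through.** No document states a recommendation rate, a target or an SSD share, so there is no planned figure to reproduce. The check is a comparison of the text followed by a bound.

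**Text**

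| Element | Diagnoses covered | Source |
|---|---|---|
| Satisfaction objective | Conductive, SSD, mixed | Protocol 6.1.2 |
| Recommendation item | Conductive only, as worded | Protocol, Appendix B |
| SSD as indicated | Profound sensorineural loss in one ear, other ear normal | Protocol Synopsis and 8.3 |
| Planned summary of the item | All subjects together, and by APHAB version | SAP 7.10.5 |
| Diagnosis subsets | Primary effectiveness endpoint only | SAP 7.10.1 |

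The item is narrower than its objective, and no summary named in the SAP text separates the group that it does not fit.

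**Bound on the pooled rate**

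Inputs:
- *s* = SSD share among respondents. It is not given in the documents; 10% to 40% is assumed.
- *r* = Yes rate in conductive and mixed loss. It is not given; 80% is assumed.
- *q* = Yes rate in SSD subjects. It is left free between 0 and 1, because their answers need not reflect their own experience.
- *N* = 72, the evaluable number in Protocol 13.1, used only to give a sense of the counts.

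Formula: pooled rate = (1 − *s*)·*r* + *s*·*q*. The lower end (*q* = 0) is (1 − *s*)·*r*. The upper end (*q* = 1) is (1 − *s*)·*r* + *s*. The width is *s*, whatever the value of *r*.

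| *s* | SSD subjects of 72 | Lower end | Upper end | Width |
|---|---|---|---|---|
| 10% | about 7 | 0.90 × 0.80 = 72% | 72% + 10% = 82% | 10 points |
| 20% | about 14 | 0.80 × 0.80 = 64% | 64% + 20% = 84% | 20 points |
| 30% | about 22 | 0.70 × 0.80 = 56% | 56% + 30% = 86% | 30 points |
| 40% | about 29 | 0.60 × 0.80 = 48% | 48% + 40% = 88% | 40 points |

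At a 30% share, the pooled rate could be 24 points below or 6 points above the 80% assumed for the subjects whom the item fits. These are extremes, not forecasts. They show only that the pooled figure does not limit the SSD contribution.

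**The case against.** The strongest case against the point is that it is small and partly answered by the form itself.

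- The first item asks how satisfied the subject is overall with the processor. It names no diagnosis and has five levels, so it serves the satisfaction objective directly for SSD subjects. This stands, and it limits the point to the recommendation item.
- An SSD subject can answer the item as a question about other people, and Not Sure is available. This also stands. A reader might infer that the recommendation rate is uninterpretable for the whole study population, but the documents do not support that: the item fits conductive and mixed loss.
- A reader might also infer that the wording pulls the rate down, because SSD subjects would retreat to Not Sure. The documents give no basis for a direction, since an uninformed Yes is equally possible.
- The endpoint is descriptive and non-validated, with no test or success criterion. This is correct, and no primary conclusion depends on the item.
- SAP 10.1 places table details in a separate document that was not available for this review, and Protocol 13.2 allows further exploratory analyses. A split by diagnosis may therefore exist or be added. The supportable statement is that the SAP text does not specify one.

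None of this removes the mismatch between the item and the objective.

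**Conclusion.** The point holds in a limited form. As worded and as summarised in SAP 7.10.5, the pooled Yes rate on the recommendation item cannot be read as willingness to recommend the system for one's own kind of hearing loss, because SSD subjects are asked about a condition that is not theirs.

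The uncertainty runs in both directions and is as wide as the SSD share. The 56% to 86% range rests on the assumed 80% rate and 30% share, neither of which is in the documents. The count of respondents is also approximate: the clinic visit is for subjects still implanted (Protocol section 7), so the number completing the form may differ from 72.

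The consequence is minor. It affects one of 13 items in a descriptive secondary endpoint, leaves overall satisfaction untouched, and can be recovered from data that the study already collects.

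**What to change.** **If the form is not yet in use:** change the item to ask about another patient with a hearing problem like the respondent's own. The form is not validated, so no validated instrument is broken. Appendix B is part of the protocol, so this is an amendment that the IRB reviews and approves (Protocol 15.5).

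**If forms have already been completed:** keep the wording, because a change part-way would leave two versions of the item in one dataset. Add to SAP 7.10.5 a table of this item by implanted-ear diagnosis (conductive, mixed, SSD). Show all groups, with a note that the wording does not match the SSD indication. Do not restrict the reported percentage to conductive and mixed loss, since that would drop a group that the objective includes.

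Diagnosis by ear is already tabulated (SAP 7.7), so no new data are needed. The form is completed once per subject and implants may be bilateral (Protocol section 7), so the table needs a stated rule for any subject whose two implanted ears have different diagnoses.

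**Cost:** a small amendment, or one extra table in which the SSD column may be small and its percentage imprecise.

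### Eight of the 13 satisfaction items ask how satisfied the subject is but offer only a frequency scale, so the feature-level satisfaction results will be hard to interpret

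*Protocol*

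**What the plan says.** Subject satisfaction is a secondary objective (Protocol 6.1.2; SAP 4.2.3). It is measured by questions that Protocol 6.2.2 itself calls non-validated, listed in one bullet with the APHAB.

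Appendix B of the Protocol holds the form. It opens with four stand-alone questions, among them "Overall, how satisfied are you with your Sophono processor" and "How satisfied or dissatisfied are you with the appearance of the hearing device", which both carry a five-point scale from Very Satisfied to Very Dissatisfied. A block of nine feature rows follows, under the instruction "For each feature, please indicate how satisfied you are with that feature". The first row reads "Overall comfort of device Always Sometimes Never", and seven more rows use the same three options. The remaining row, "Do you use a different strength for physical activities", is answered Yes or No.

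For analysis, SAP 7.10.5 plans "descriptive statistics to summarize results of the questionnaires overall and by each item", with counts and percentages for categorical variables. One of its planned tables covers subject satisfaction together with product features. It gives no scoring rule and does not map the three options to levels of satisfaction.

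**The concern.** The instruction asks for a degree of satisfaction and the options give a frequency. Respondents must supply the link themselves, and they may not all supply the same one. For "Visibility to others", a tick at Always could mean that the subject is always satisfied with how visible the device is, or that the device is always visible. For a cosmetic feature those point in opposite directions, and nothing recorded on the form would show which was meant.

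The feature rows are the only place where the study asks about satisfaction with comfort, sound quality, durability and magnet strength one at a time. Followed as written, the plan would report percentages of Always, Sometimes and Never under a satisfaction heading, without an agreed meaning for those words. A reader of the final report could take them as satisfaction rates.

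**Working it through.** The documents state no item count or score to reproduce, so the check is a count of items and response sets in Appendix B, followed by a row-by-row look at direction.

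**Step 1: items and options.**

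| Item | Options | Do the options fit the question? |
|---|---|---|
| Overall satisfaction | 5-point satisfaction | Yes |
| Would recommend | Yes / No / Not Sure | Yes |
| Appearance | 5-point satisfaction | Yes |
| Ease of operation | 5-point ease | Yes |
| Comfort | Always / Sometimes / Never | No |
| Visibility | Always / Sometimes / Never | No |
| Clearness of sound | Always / Sometimes / Never | No |
| Durability | Always / Sometimes / Never | No |
| Reliability | Always / Sometimes / Never | No |
| Magnet strength, daily | Always / Sometimes / Never | No |
| Magnet strength, physical activity | Always / Sometimes / Never | No |
| Different strength used | Yes / No | Yes (a question about use) |
| Locating sounds | Always / Sometimes / Never | No |

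**Step 2: counts.**

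- Total items: 4 + 9 = 13.
- Mismatched rows: 9 − 1 = 8.
- Share of the form: 8/13 = 61.5%.
- Share of the feature block: 8/9 = 88.9%.
- Share of the items that ask for satisfaction (2 stand-alone + 8 rows = 10): 8/10 = 80%.
- Unaffected items: 13 − 8 = 5 (two satisfaction, one ease, one Yes/No/Not Sure, one Yes/No).

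The mismatch recurs in every one of the eight rows, across a page break, so it does not look like a fault of text extraction.

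**Step 3: direction.** Take two ways a subject could read Always: (A) always satisfied with the feature; (B) the feature is always so.

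- Comfort, clearness, durability, reliability, locating sounds (5 rows): A and B both run in the favourable direction, though B is awkward for durability. Direction is tolerably clear. Degree is not.
- Visibility (1 row): A is favourable and B is plausibly unfavourable. Direction is ambiguous.
- Magnet strength, daily and physical (2 rows): A is favourable. B has no settled meaning, since always strong enough and always too strong are both open. Direction is plausibly ambiguous.

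5 + 1 + 2 = 8, so the loss of gradation affects all eight rows and uncertain direction affects up to three.

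**Step 4: does the SAP resolve it?** No. SAP 7.10.5 contains no mapping or item-level reading rule, and SAP 7.6 lists no derived satisfaction variable. SAP 10.1 refers table details to a separate document that is not available here.

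**The case against.** The best case for the plan has four parts.

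- **The instruction governs the rows.** Because the block asks how satisfied the subject is, the natural reading is always, sometimes or never satisfied: crude, but ordered. This has force, particularly for comfort, clearness, reliability and locating sounds. A reader might infer from the mismatch that the satisfaction endpoint cannot be interpreted at all. The documents do not support that, since counts can be tabulated and a sensible reading exists. What stands is that the form does not state that reading, that it is weakest for visibility and magnet strength, and that even under it no one can record neutrality or a degree of dissatisfaction.
- **The item that answers the objective directly is sound.** Overall satisfaction has a proper five-point scale. Recommendation, appearance and ease also work, and appearance partly covers the visibility row. This stands. The 62% is a share of items, not a weight in any score.
- **No pooled score is specified.** A reader might infer from the word overall in SAP 7.10.5 that unlike scales will be combined. The same section goes on to summarise the overall set of patients, so overall may mean all patients. Mixing of scales is a possibility to guard against, not something that the plan prescribes.
- **The stakes are low and a change splits the data.** The questions are openly non-validated, the analysis is descriptive, and the form is given only at the prospective visit (SAP 5.3), so a new version divides a small sample. All true. But disclosing a lack of validation does not make options fit a question.

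A lighter remedy would be to state that the options mean always, sometimes or never satisfied. Printed on the form, that would settle direction for future respondents but leave the scale without gradation. Added only to the SAP, it could not show how earlier respondents had read the rows.

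**Conclusion.** The point holds for the feature-level part of the satisfaction endpoint. Eight of 13 items pair a satisfaction question with a frequency scale. All eight lose gradation and any neutral or dissatisfied option. One (visibility) is clearly ambiguous in direction, and two (magnet-spacer strength) plausibly are.

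The four stand-alone items, the Yes/No row, the APHAB, and both primary endpoints are untouched. No test, threshold or sample-size figure depends on these rows. It is a defect worth correcting in a descriptive secondary endpoint.

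The conclusion assumes that Appendix B is the form given to subjects, and that no scoring rule exists in the separate table specification. If such a rule exists, it would settle how the counts are labelled, but not how subjects understood the options.

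**What to change.** **Forms not yet completed.** In the eight rows, replace Always/Sometimes/Never with the five-point Very Satisfied to Very Dissatisfied scale already used on the same form. Leave the Yes/No row as it is. Update the eCRF codes and submit the change for IRB review, as Protocol 15.5 requires for amendments.

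**Forms already completed.** Keep and report the data. In SAP 7.10.5, specify:

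- raw counts item by item, shown separately from the new version;
- a footnote that the options do not match the question;
- a flag on visibility and the two magnet-spacer strength rows as ambiguous in direction;
- no combination of these eight rows with the other items, if any overall questionnaire summary is produced.

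A reader might infer that answers on completed forms should be discarded or barred from any conclusion. That goes further than needed, because item-level counts remain usable with the caveat.

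**Cost.** The form change is one block of a non-validated questionnaire, with its codes and an IRB submission. It adds no visit, test or subject. The downside is that the two versions are not comparable on these eight items. With about 100 subjects planned, and about 75 forms if the planning dropout of 25% all falls before the visit (100 × 0.75 = 75), each version would hold only part of a small sample. The documents do not say how many forms are already complete. If data collection has ended, only the reporting changes apply, and they need no change to the form.
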